While numerous studies have investigated the broader implications of health education interventions on vaccination awareness and rates, there remains a distinct lack of focused research specifically targeting primary school students, especially within the context of China.¹⁰⁻¹² The unique age group, characterized by their transitional cognitive abilities and susceptibility to influence, may respond differently to health literacy interventions than other age cohorts. Moreover, regional differences, cultural practices, and local health infrastructure in China might further impact the effectiveness of such interventions. Thus, this study aims to investigate the influence of health education on influenza vaccination rates and the level of influenza vaccination health literacy among fourth and fifth-grade primary school students. The methodological approach will involve a cluster randomized trial with schools serving as the unit of analysis. The findings will provide a scientific basis for future interventions.

METHODS AND ANALYSIS

Study objectives

This study seeks to explore the impact of health education interventions on vaccination and influenza vaccination awareness among senior primary school students. By evaluating the impact of health education on the seasonal influenza vaccination rate and the level of influenza vaccination health literacy, we aim to provide a scientific foundation for regional influenza prevention and control

strategies. The specific objectives of this research are: 1) To ascertain the rate of influenza infection, the status of influenza vaccination, and the level of health literacy related to influenza vaccination among primary school students in Dongguan City. 2) To compare and contrast the influenza vaccination rate and the level of influenza vaccination health literacy between the experimental and control groups, thereby evaluating the impact of health education intervention on these parameters. 3) To assess the efficacy of influenza vaccine immunization among primary school students in Dongguan City.

Study design

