The study employs a multi-stage cluster sampling method. In the first stage, one central urban area (tentatively identified as Dongcheng Street, which oversees 31 primary schools) and one non-central urban area (tentatively identified as Gaobu Town, which oversees 13 primary schools) will be randomly selected, reflecting the urban-rural structure of Dongguan City. In the second stage, ten primary schools will be randomly selected from each administrative district, with five designated as intervention group schools and the remaining five as control group schools. This results in a total of twenty primary schools, evenly split between the intervention and

control groups. In the third stage, two classes from each of the two grades (fourth and fifth grades) are randomly selected from each of the twenty selected schools using a cluster sampling method, with surveys conducted at the class level. Each school comprises a minimum of 152 students. Schools with 152 students will have one additional class randomly selected. The final estimated total sample size is projected to be 3036. Random sampling and randomized grouping are achieved using computer software to generate random numbers. The sample size is determined using the following formula:

$$n = \frac{\left\{ z_{1-\alpha/2} \sqrt{2(m-1)\rho + 2} + z_{\beta} \sqrt{m\rho + 1} \right\}^2 * \{p_1(1-p_1) + p_2(1-p_2)\}}{(p_1 - p_2)^2}$$

where: n is the desired sample size for each cohort, $z_{1-\alpha/2}$ is the value corresponding to the accepted Type I error rate (eg $z_{1-\alpha/2}$ about 1.96 for an error rate of 0.05), z_{β} is the value corresponding to the desired statistical power, e.g., for a power of 0.8, z_{β} is approximately 0.84. m is the size of each cohort, ρ is the intra-group correlation coefficient, p_1 is the expected outcome rate in the test group (ie, influenza vaccination rate), and p_2 is the expected outcome rate in the control group. Based on the assumption that the anticipated influenza vaccination rate is 80% in the intervention group and 50% in the control group, the estimated sample size, denoted as 'n', is 138 students per school.^{13, 14} This implies that approximately 138 primary school students are required for each group, yielding a total sample size of 2760 individuals. To account for potential sample attrition, the sample size is expanded by 10%, resulting in a final estimated total sample size of 3036 for statistical analysis.

Intervention methods

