The intervention group will receive a health education intervention focused on

influenza vaccination literacy, while the control group will continue with their standard school health education without any additional intervention. An influenza vaccination health education including topics such as the importance of influenza vaccination, benefits of vaccination, and vaccination methods, will be developed and reviewed by an expert group. The package for the intervention group will include educational activities, distribution of promotional materials, vaccination services, and distribution of vaccination souvenirs. The details are as follows:

1) Educational activities include classroom lectures and parent meetings. Medical professionals or public health experts will be invited to deliver lectures at the school, providing detailed information on the role and benefits of influenza vaccination and the risks of influenza. Teachers and relevant school staff will be trained to understand the importance of influenza vaccination, reinforcing these messages in everyday teaching. Content about influenza vaccines will be incorporated into school health education courses, facilitating student learning about influenza vaccines. In addition, Teachers will discuss the importance of the flu vaccine at parent meetings, encouraging parents to facilitate their children's vaccination.

2) Promotional materials include educational booklet, animated videos, vaccination service and vaccination souvenirs. Educational booklet will be designed and distribute to students to raise their awareness of flu vaccines. Animated videos will be created to explain the effects of flu vaccines and the benefits of vaccination in an easy-to-understand manner. These videos will be played on school TVs or computers, and students will be organized to watch them. Influenza vaccination services will be provided to students who have no contraindications to influenza vaccination, are in

good health, and are 4-6 months post their last influenza vaccination, based on the principle of informed consent, voluntariness, and self-payment. 'Epidemic Prevention Little Guards' medals will be created and distributed to vaccinated students as a commemorative incentive to encourage vaccination.

Intervention time

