Primary outcomes include the influenza vaccination rate and the influenza vaccination health literacy level. The influenza vaccination rate will be calculated as the number of vaccinated individuals divided by the total number of individuals, multiplied by 100%. Regarding the influenza vaccination health literacy level, each correct answer for the scale will be scored as one point, with incorrect answers receiving no points. Based on the scores, health literacy levels will be categorized as low, medium, or

high.

Secondary outcomes include influenza incidence, the ILI incidence and the influenza vaccine protection rate. The influenza incidence will be calculated as the number of individuals diagnosed with influenza divided by the total number of individuals, multiplied by 100%, The ILI incidence will be calculated as the number of ILI cases divided by the total number of participants, multiplied by 100%. The influenza vaccine protection rate will be calculated as the difference between the incidence rate in unvaccinated individuals and the incidence rate in vaccinated individuals, divided by the incidence rate in unvaccinated individuals, multiplied by 100%.

Statistical analysis plan

Continuous variables will be described using means \pm standard deviation or median (interquartile range), and comparisons will be made using two independent samples t-tests or Wilcoxon rank-sum tests. Categorical variables will be described using frequency and composition ratios, and rate comparisons will be conducted using Chi-square tests or Fisher's exact probability method. The association between the level of influenza vaccination health literacy and vaccination willingness will be analyzed using multivariate logistic regression.

Quality control

Quality Control will be conducted in accordance with the requisite quality control standards, with dedicated on-site quality control personnel assigned to oversee investigation and evaluation. These personnel should be proficient in various testing technical requirements and quality control points, and familiar with the on-site

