Blinding (masking)	17a	Who will be blinded after assignment to interventions (eg, trial participants, care providers, outcome assessors, data analysts), and how	N/A
	17b	If blinded, circumstances under which unblinding is permissible, and procedure for revealing a participant's allocated intervention during the trial	N/A

Methods: Data collection, management, and analysis

Data collection methods	18a	Plans for assessment and collection of outcome, baseline, and other trial data, including any related processes to promote data quality (eg, duplicate measurements, training of assessors) and a description of study instruments (eg, questionnaires, laboratory tests) along with their reliability and validity, if known. Reference to where data collection forms can be found, if not in the protocol	10-12, Appendix I-II
-------------------------	-----	--	----------------------

	18b	Plans to promote participant retention and complete follow-up, including list of any outcome data to be collected for participants who discontinue or deviate from intervention protocols	N/A
Data management	19	Plans for data entry, coding, security, and storage, including any related processes to promote data quality (eg, double data entry; range checks for data values). Reference to where details of data management procedures can be found, if not in the protocol	10-13
Statistical methods	20a	Statistical methods for analysing primary and secondary outcomes. Reference to where other details of the statistical analysis plan can be found, if not in the protocol	13
	20b	Methods for any additional analyses (eg, subgroup and adjusted analyses)	N/A
	20c	Definition of analysis population relating to protocol non-adherence (eg, as randomised analysis), and any statistical methods to handle missing data (eg, multiple imputation)	N/A
Methods: Monitoring			
Data monitoring	21a	Composition of data monitoring committee (DMC); summary of its role and reporting structure; statement of whether it is independent from the sponsor and competing interests; and reference to where further details about its charter can be found, if not in the protocol. Alternatively, an explanation of why a DMC is not needed	13
	21b	Description of any interim analyses and stopping guidelines, including who will have access to these interim results and make the final decision to terminate the trial	N/A

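### The vaccine protection rate, the only planned answer to Objective 3, is an unadjusted contrast of self-selected children and should be adjusted within school and reported as observational effectiveness

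*Combined protocol and SAP*

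**What the plan says.** - **Objective.** Study objectives, item 3: "To assess the efficacy of influenza vaccine immunization among primary school students in Dongguan City".
- **Outcome.** Under Study outcomes, the protection rate is "the difference between the incidence rate in unvaccinated individuals and the incidence rate in vaccinated individuals", divided by the unvaccinated incidence. Influenza incidence is "the number of individuals diagnosed with influenza divided by the total number of individuals", so it is a cumulative proportion without person-time. Confirmed influenza and influenza-like illness (ILI) are both defined; the plan does not say which one enters the protection rate.
- **How children come to be vaccinated.** Intervention methods: "The package for the intervention group will include educational activities, distribution of promotional materials, vaccination services", together with souvenirs. The service is offered "based on the principle of informed consent, voluntariness, and self-payment". Control schools keep routine health education.
- **Analysis.** The Statistical analysis plan lists t or Wilcoxon tests and chi-square or Fisher tests. Its one regression serves another question: "The association between the level of influenza vaccination health literacy and vaccination willingness will be analyzed using multivariate logistic regression". Item 20b of the SPIRIT checklist (Appendix IV), which covers adjusted analyses, is marked N/A.
- **Timing.** Under Intervention time, CDC staff visit in the first month, toolkit activities run from September 2023 to January 2024, and follow-up is in February 2024. Both questionnaires (Appendices I and II) ask when the child was vaccinated, for 2023 only. No outcome definition uses the date.

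**The concern.** Schools are randomised to an education package; children are not randomised to vaccine. A family that pays for a dose may differ from one that does not in income, parental education, the child's health or earlier vaccination, and any of these may relate to influenza risk or to the chance of being diagnosed. Because coverage is expected to differ by arm, vaccination status is also tied to school. The crude formula attributes all such differences to the vaccine.

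A second, conditional issue is timing. With no rule for when a child starts to count as vaccinated, a case before the dose could be placed in either group, and a case soon after it would count against the vaccine even if protection had not yet begun.

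At stake is the whole answer to one stated objective, in a study whose results are to go to health departments. A reader would take the figure as vaccine efficacy.

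**Working it through.** The documents give no expected value or precision for the protection rate, so there is no figure to reproduce. The only input taken from them is coverage: "the anticipated influenza vaccination rate is 80% in the intervention group and 50% in the control group". Every other input below is an assumption chosen to show scale.

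**1. Arm mix (equal arms).**
- Share of vaccinated children in intervention schools: 0.8 / (0.8 + 0.5) = 62%.
- Share of unvaccinated children in intervention schools: 0.2 / (0.2 + 0.5) = 29%.
- Let r be the incidence ratio, intervention to control, for reasons other than the child's own dose. A useless vaccine then reads 1 - [(0.8r + 0.5)/1.3] / [(0.2r + 0.5)/0.7].
- r = 0.8: 1 - 0.877/0.943 = 7%. r = 0.7: 1 - 0.815/0.914 = 11%. r = 1.25: 1 - 1.154/1.071 = -8%. r = 1: 0%.

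**2. Adding one child-level factor.** Assume that half the children carry it, with coverage 10 points above their arm's rate (90% and 60%) and the others 10 points below (70% and 40%). Control children without the factor have 10% incidence if unvaccinated.
- Arm ratio 0.7, factor hazard ratio 0.67, useless vaccine. Incidences are 1 - 0.9^0.469 = 4.8% and 1 - 0.9^0.7 = 7.1% in intervention schools (with, without the factor), and 1 - 0.9^0.67 = 6.8% and 10% in control schools.
- Vaccinated: (0.9×4.8 + 0.7×7.1 + 0.6×6.8 + 0.4×10)/2.6 = 6.7%. Unvaccinated: (0.1×4.8 + 0.3×7.1 + 0.4×6.8 + 0.6×10)/1.4 = 8.1%. Reading: 17%. A true 50% hazard reduction reads 58%.
- Arm ratio 1.3, hazard ratio 1.5: a useless vaccine reads -18%, and a true 50% reads 39%.

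**3. Timing, without confounding.** Assume a 10% attack rate, a flat season from October to January, and doses spread evenly over September to November. Cumulative hazard is -ln 0.9 = 0.1054.
- No-bias benchmark: 1 - (1 - 0.9^0.5)/0.1 = 49%.
- The third dosed in September lose none of the season before the dose. The other two thirds lose 0 to 1/2 of it, 1/4 on average. The overall mean is 2/3 × 1/4 = 1/6.
- All cases classified by final status, true 50%: relative hazard 1/6 + 0.5 × 5/6 = 0.583; vaccinated incidence 1 - exp(-0.1054 × 0.583) = 5.96%; reading 1 - 5.96/10 = 40%.
- If a share f of children infected before the planned dose forgo it, a useless vaccine looks protective. With q = 0.0173 infected before the dose and intended coverage p, I_vacc = (0.1 - fq)/(1 - fq) and I_unvacc = [(1 - p)0.1 + pfq]/[(1 - p) + pfq]. For f = 10%, p = 50%: 0.0984 against 0.1016, reading 3%. For f = 100%, p = 80%: 0.0842 against 0.1581, reading 47%.

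**4. All doses in September.**
- Season flat from September: 1/10 of it precedes the dose on average; relative hazard 0.1 + 0.5 × 0.9 = 0.55; incidence 1 - exp(-0.1054 × 0.55) = 5.63%; a true 50% reads 44%. With q = 0.0105, a useless vaccine reads 2% to 34% over the same range of f and p.
- Season from October, with protection about two weeks after the dose: a true 50% reads 47%, against 49%.

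**The case against.** Several points on the other side have force.

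- **Schools are randomised within district.** Arm incidence is therefore equal in expectation unless the package changes influenza or its detection in other ways, coverage protects classmates indirectly, or 20 schools are imbalanced by chance. This stands. A reader might infer that the 62% to 29% split is itself a bias; it becomes one only if r differs from 1. Child-level self-selection does not need that condition.
- **Almost every magnitude is assumed.** This stands. A reader might infer that the plan must overstate protection; the calculations go both ways. For an effective vaccine the two timing mechanisms also oppose each other. In the three-month case at 65% coverage, a true 50% reads 40% if no infected child forgoes the dose and 66% if all do.
- **The package visit is in the first month, so timing may not matter.** Partly right: doses completed before influenza circulates, with no lag to protection, give no timing bias. But September dosing alone does not guarantee this (step 4). The October onset in the Introduction refers to various regions of China, and no Dongguan season is given.
- **Dates may be in hand.** A reader might infer that no dose dates are collected or scheduled. The forms do ask for 2023 dates. The text has no dose schedule, but Figure 2, the timeline, is not available to this review and may contain one. What the text lacks is an analysis rule.
- **The outcome is secondary.** True, and this limits the weight of the point. It is still the only planned answer to Objective 3.

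**Conclusion.** The concern holds on confounding: as written, the protection rate is an unadjusted comparison of children who did and did not take a self-paid vaccine, and it cannot support a statement about efficacy. This follows from the text and does not depend on the illustrations. Its actual size cannot be derived from the documents. Under the assumed ratios, arm mix alone moves a useless vaccine to between -8% and 11%, and one added child-level factor widens that to between -18% and 17%.

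Timing is a conditional sub-point: it biases the result only if cases occur before protection begins, and neither the season nor the dose schedule can be settled from the text.

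A reader might infer that the trial's main result is compromised. It is not by this point: the comparisons of vaccination rate and health literacy follow the randomised arms and do not use this formula. This is a change that should be made, and a cheap one.

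**What to change.** 1. **Name the incidence.** Analyse confirmed influenza and ILI separately.
2. **Compare within school and adjust.** Replace the crude formula with a model using school strata or school terms, which also cover arm and district, so that the arm mix in step 1 drops out. Add a short pre-specified covariate set already collected, such as grade or age, prior vaccination, family income or parental education, and disease history. Use standard errors that allow for school clustering. Pre-specify a reduced model (school plus one or two covariates, or a propensity score) for few cases: at an assumed 1% to 2% confirmed incidence, 3036 children give about 30 to 61 cases over 20 schools. State that a within-school estimate measures direct effect and excludes indirect protection between schools.
3. **Use dates where usable.** Treat vaccination as time-varying on a calendar time axis, from dose date plus a pre-specified lag, with earlier time and cases counted as unvaccinated. Extend the date item to January and February 2024. If dates are not usable, items 1, 2 and 4 still apply.
4. **Relabel.** Report observational vaccine effectiveness, not efficacy, and state residual self-selection as a limitation.

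**Cost.** Extra programming, one extended questionnaire item, onset or test dates requested from the CDC network, and record linkage. The child ID on the parent form and the name and date on the clinic register help, although the listed student form shows only class, gender and age. Some precision is lost, because a school with no cases adds no information.

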The proposed study is a cluster randomized controlled trial. Two administrative districts, one in the central urban area and the other in the non-central urban area of Dongguan, will be selected for this study. Within each district, ten primary schools will be randomly selected, with half designated as intervention group schools and the remaining half as control group schools. This results in a total of twenty primary schools, evenly split between the intervention and control groups.

The intervention group will receive a health education intervention focused on influenza vaccination, while the control group will continue with their routine school health education. The intervention period for this study is projected to last approximately three to four months. Data collection will conduct at the onset and conclusion of the intervention period. The primary outcomes of interest are the differences in influenza vaccination rates and influenza vaccination health literacy levels between the experimental and control groups, which will be used to evaluate

the effectiveness of the intervention. The overview of the study procedure is shown in the Figure 1.

Study sample

Study participants are primary school students in grades 4 to 5 in Dongguan City.

Inclusion criteria include: 1) Primary school students within the age range of 7-12 years. 2) Students and their parents who voluntarily agree to participate in the study and provide signed informed consent. 3) Permanent residents of Dongguan City who are expected to complete the project without transferring schools during the study period.

In addition, individuals with contraindications to influenza vaccination, who have recently received an influenza vaccination, diagnosed with influenza or confirmed as influenza-like cases at the commencement of the study, or unwilling to participate in the project, will be excluded.

Sampling method

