Staff of the affiliated street Center for Disease Prevention and Control (CDC) will visit the school in the first month to implement intervention activities using the health education intervention package. The intervention period will commence in September 2023 and conclude in February 2024, resulting in a total intervention duration of approximately three to four months. The specific intervention process is as follows: 1) At the start of the semester (early intervention stage in September 2023), initiation activities will be conducted. The investigators will introduce the study to teachers and students, and medical professionals or public health experts will be invited to deliver classroom lectures at the intervention group schools. Baseline data will be collected at this stage. 2) During the intervention period (September 2023 – January 2024), the intervention group will follow the health education intervention toolkit to conduct intervention activities. 3) At the conclusion of the semester (February 2024), follow-up data will be collected. The intervention timeline is shown in the Figure 2.

Data collection and analysis

Questionnaire surveys will be administered to students and parents before and after

the intervention, using self-completion. The questionnaire design, which is informed by similar research literature (Appendix 1 & 2), will undergo evaluations for reliability and validity. The questionnaire will include the following content: 1) Socio-demographic characteristics (name, age, sex, class, residential address, parents' educational level, occupation, family income); 2) Personal history (basic disease history, allergy history, and personal history); 3) Influenza vaccination health literacy level. The health literacy level concerning influenza vaccination will be assessed across four dimensions: knowledge, attitude, behavior, and skills related to influenza vaccination. Details of these four dimensions include knowledge of basic facts about the influenza vaccine (such as its efficacy, vaccination frequency, and side effects), attitudes towards the influenza vaccine (including perceptions of its efficacy and safety), behavioral characteristics related to influenza vaccination (such as willingness to be vaccinated, vaccination status, and timing of vaccination), and sources of information about the influenza vaccine.

Confirmation of influenza and surveillance of influenza-like cases

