Do you think the flu vaccine needs to be given every year to

prevent the flu?

Do you think getting a flu vaccine is good for you and your child's health?

Do you think it is necessary to get a flu vaccine?

Are you confident that the flu vaccine is safe?

Behavioral questions

Within the last year, have you ever had influenza (or had a sudden onset of illness with a high fever $\geq 38^{\circ}\text{C}$ accompanied by flu-like symptoms such as generalised malaise, myalgia, sore throat, etc.)?

If yes, when was the last time you had influenza (or had a sudden onset of illness with high fever $\geq 38^{\circ}\text{C}$ accompanied by influenza-like symptoms such as generalised malaise, myalgia, sore throat, etc.)?

Has your child had influenza (or had a sudden onset of illness with high fever $\geq 38^{\circ}\text{C}$, accompanied by flu-like symptoms such as generalised weakness, myalgia, sore throat, etc.) within the last year?

If yes, when was the last time your child had influenza (or had a sudden onset of illness with a high fever $\geq 38^{\circ}\text{C}$ accompanied by influenza-like symptoms such as generalised malaise, myalgia and sore throat)?

Have you taken your child for a flu vaccination between 2020 and 2022?

Have you or your spouse been vaccinated against flu in 2023?

If you have been vaccinated against flu, when did you or your spouse get the flu vaccine this year?

Has your child been vaccinated against flu in 2023?

If your child has been vaccinated against flu, when did your

child get the flu vaccine this year?

If your child has been vaccinated against flu, why did you decide to take your child for a flu vaccination this year?

If your child hasn't been vaccinated against flu, why did you decide not to take your child for a flu vaccination this year?

If your child has not had a flu vaccination this year, are you currently willing to take your child to get one?

Would you be willing to take your child for a flu vaccination in the future?

Would you like to recommend that others get the flu vaccine?

Skill Questions

Do you know how to schedule your flu vaccine?

Do you take an active interest in information about flu vaccinations?

Where do you get information about flu vaccinations?

Appendix II Questionnaire for Health Literacy Study of Influenza Vaccination among Primary School Students in Dongguan City (Student Version)

Question

Basic information

Your class?

Your gender?

How old are you?

knowledge questions

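### The arm comparisons use neither baseline literacy, prior vaccination nor district, which gives up precision relative to a cluster-correct adjusted analysis and leaves chance baseline differences between 20 schools unadjusted

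*Combined protocol and SAP*

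**What the plan says.** The data and the design structure needed for adjustment are already in the protocol:

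- **Baseline literacy.** Under Data collection and analysis: "Questionnaire surveys will be administered to students and parents before and after" the intervention.
- **Prior vaccination.** The parent form (Appendix I, behavioral questions) asks: "Have you taken your child for a flu vaccination between 2020 and 2022".
- **District.** Under Study design: "Within each district, ten primary schools will be randomly selected, with half designated as intervention group schools", the other half being controls. Sampling method repeats this as five and five.

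The Statistical analysis plan uses none of the three to compare arms. For continuous variables, "comparisons will be made using two independent samples t-tests or Wilcoxon rank-sum tests". For proportions, "rate comparisons will be conducted using Chi-square tests or Fisher's exact probability method". The vaccination rate falls under the second sentence. Literacy falls under either, because Study outcomes defines a point score and then groups it into three levels. The only regression relates literacy to willingness to be vaccinated and is not an arm comparison. The SPIRIT checklist (Appendix IV) marks item 20b, which covers adjusted analyses, as not applicable.

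**The concern.** Only 10 schools are allocated to each arm. Randomisation of so few units can leave the arms visibly different at baseline, and an unadjusted follow-up comparison carries such a difference into the estimate to the extent that it predicts the outcome. Where baseline values predict follow-up, a model that includes them also gives a narrower valid interval from the same schools. A restriction used in allocation, here district, belongs in the model so that the error term matches the design. Covariates named in advance are credible; covariates chosen after a baseline difference has been seen are much less so.

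**Working it through.** **The plan's own figures.** Sampling method gives 138 pupils per school. Then 138 × 20 = 2760 and 2760 × 1.10 = 3036, both as stated. The 138 itself cannot be checked, because the formula's cluster size m and correlation ρ are given no values. With the printed formula, rates of 80% and 50%, z = 1.96 and z = 0.84, 138 requires ρ of about 0.0096 if m = 138, or about 0.036 if m = 38 (152 pupils over four classes). I take 138 per school and 10 schools per arm from the plan. Every ICC, baseline/follow-up correlation and R² below is an assumption.

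**Chance difference between arms at baseline.** In SD units, SE = √[(2/10) × (ICC + (1 − ICC)/138)]. For a proportion near 50% (assumed), one SD is 50 percentage points.

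| ICC | SE (SD units) | SE, prior vaccination (points) | 95% range (points) | P(literacy gap > 0.2 SD) |
|---|---|---|---|---|
| 0.02 | 0.074 | 3.7 | ±7.2 | 0.7% |
| 0.05 | 0.107 | 5.3 | ±10.5 | 6% |
| 0.10 | 0.146 | 7.3 | ±14.3 | 17% |

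Example at ICC 0.05: √[0.2 × (0.05 + 0.95/138)] = √0.01138 = 0.107. At the two ρ values implied by the plan's 138, the SD for prior vaccination is 2.9 and 4.6 points.

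**Precision, against a valid unadjusted school-level analysis.** Twenty school means in two arms leave 18 df. With q covariates that explain a share R² of the variance between school means, the interval-width ratio is √(1 − R²) × t(0.975, 18 − q)/t(0.975, 18). For q = 2 (district and one baseline covariate), t is 2.120 on 16 df against 2.101 on 18 df, a factor of 1.009:

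- R² = 0.10: 0.949 × 1.009 = 0.96, worth about 20/0.90 = 22 schools.
- R² = 0.25: 0.866 × 1.009 = 0.87, worth about 20/0.75 = 27 schools.
- R² = 0.50: 0.707 × 1.009 = 0.71, worth about 20/0.50 = 40 schools.
- R² = 0: 1.004, 1.009 or 1.015 for q = 1, 2 or 3.

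R² here is a school-level quantity. At ICC 0.05, true between-school variance is 0.05/(0.05 + 0.95/138) = 88% of the variance of a school mean, so a correlation between individual pupils' scores does not supply it.

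**Literacy, by simulation of school means.** Assumptions: ICC 0.05, effect 0.3 SD, a 0.2 SD gap between districts, 138 per school.

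| School-level model | Mean 95% interval width (SD) | Power |
|---|---|---|
| Unadjusted | 0.48 | about 0.70 |
| + district | 0.44 | about 0.75 |
| + district + baseline mean, correlation 0.3 | 0.43 | about 0.77 |
| Same, correlation 0.5 | 0.40 | about 0.84 |
| Same, correlation 0.7 | 0.34 | about 0.93 |

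With no effect, the unadjusted school-level test rejects about 3% of the time. It is conservative because the district gap inflates its error term. Adding district restores about 5%.

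**Vaccination, school-level power.** At the planned contrast, "anticipated influenza vaccination rate is 80% in the intervention group and 50% in the control group", unadjusted power is already about 0.99 or more up to ICC 0.10, and 0.87 at ICC 0.20. At a 15-point difference (65% versus 50%) and ICC 0.05 it is 0.78, rising to 0.88 at R² 0.25 and 0.97 at R² 0.50.

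**The case against.** Several objections have force and limit the point.

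1. **The plan's intervals are not too wide.** A reader might infer from the missing adjustment that the listed tests give wider intervals than necessary. Applied to individual pupils they do the opposite, because they ignore clustering. At ICC 0.10 the design effect is 1 + 137 × 0.10 = 14.7, so the standard error is understated about √14.7 = 3.8-fold. The precision gain exists only against an unadjusted analysis that respects schools. The Introduction names schools as the unit of analysis, but the Statistical analysis plan does not carry this through; read at school level, the tests are still unadjusted. Ignored clustering is a separate and larger problem that covariates alone would not cure.
2. **A serious imbalance is not the expected result.** The probability of a literacy gap above 0.2 SD is 0.7% to 17% over the ICCs shown. Chance imbalance under randomisation is not bias, and a valid cluster-level interval allows for it.
3. **District cannot be imbalanced.** The 5:5 split prevents it.
4. **A single size cannot be quoted.** The 7.3-point SD belongs to one assumed ICC. The rule that adjustment multiplies variance by 1 − r² needs a school-level correlation, which the documents do not give, and does not carry over directly to a binary outcome.
5. **The baseline may not be clean or linkable.** Intervention time places baseline collection in the same opening stage as the first lectures. If it follows a lecture, adjustment could remove part of the effect. The student form lists class, gender and age but no identifier, although the main text lists name.
6. **At the planned vaccination effect, power is ample without adjustment.**

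What remains is that no arm comparison uses covariates the trial already collects or the factor within which schools were allocated. Objection 5 is met by stating the order of collection and, where forms cannot be linked, by using school baseline means.

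**Conclusion.** The point holds as a recommended improvement; it does not by itself invalidate the plan. Relative to a cluster-correct unadjusted analysis, the comparison of both primary outcomes gives up precision and leaves chance differences in baseline literacy and prior vaccination unadjusted. Leaving out district affects precision and the error term only.

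The size depends on quantities that the documents do not supply, so the results above are a range to plan against and not an estimate for this trial. The possible loss is small if the covariates turn out useless, and the possible gain is worth having if they predict even moderately. It matters most for literacy, which has no stated effect size or power calculation, and for vaccination effects well short of 30 points. The documents do not support a claim that the results will be biased, or that the intervals from the plan as written will be too wide.

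**What to change.** Rewrite the primary arm comparisons in the Statistical analysis plan as school-level, mixed or GEE models, with a small-sample correction for 20 clusters.

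- **Literacy:** follow-up score on arm, baseline score and district. Use the school baseline mean if student forms cannot be linked. Keep the score as the modelled outcome; the three levels can be reported descriptively.
- **Vaccination:** vaccinated or not on arm, parent-reported 2020-2022 vaccination and district, reported as a risk difference so that adjustment does not change the measure being estimated. The 2020-2022 item is more usable than the 2023 one, because recently vaccinated children are excluded at entry.
- **Baseline:** state that it is collected before the first lecture, and how student forms are linked.
- **Supportive:** report unadjusted cluster-level results alongside.

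Update SPIRIT item 20b to match. The cost is protocol wording, slightly more analysis work, and 1 to 3 of the 18 school-level degrees of freedom. No new questionnaire content is needed, but linking individual student forms requires that an identifier is in fact recorded.
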